4.2.2. Other Secondary Objectives

These are prespecified objectives that will not be adjusted for multiplicity.

Objectives	Endpoints
To test the hypothesis that baricitinib 1-mg QD, 2-mg QD, or 4-mg QD is superior to placebo in the treatment of patients with moderate to severe AD.	
 Proportion of patients achieving IGA of 0 or 1 with a ≥ 2-point improvement at Week 4
To compare the efficacy of baricitinib 1-mg QD, 2-mg QD, or 4-mg QD to placebo in AD during the 16-week double-blind placebo-controlled period as measured by physician-assessed signs and symptoms of AD.	
 Proportion of patients achieving EASI50 at 16 weeks Proportion of patients achieving IGA of 0 at 16 weeks Mean change from baseline in SCORAD at 16 weeks Proportion of patients achieving SCORAD90 at 16 weeks Mean change from baseline in BSA affected at 16 weeks Proportion of patients developing skin infections requiring antibiotic treatment by Week 16
To compare the efficacy of baricitinib 1-mg QD, 2-mg QD, or 4-mg QD to placebo in AD during the 16-week, double-blind, placebo-controlled treatment period as assessed by patient-reported outcome/QoL measures.	
 Percent change from baseline in Itch NRS at 1 week and 16 weeks Mean change from baseline in Itch NRS at 4 weeks and 16 weeks Mean change from baseline in the total score of the POEM at 16 weeks Mean change in the PGI-S-AD scores at 16 weeks Mean change from baseline in HADS at 16 weeks Mean change in the DLQI scores at 16 weeks Mean change in the WPAI scores at 16 weeks Mean change in the EQ-5D-5L scores at 16 weeks

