6.2.4. Derived Data

- Age (year), derived using first dose date as the reference start date and July 1st of birth year and truncated to a whole-year (integer) age. Patients whose derived age is less than 18 will have the required minimum age of 18 at informed confirmed; reporting for age, age groups, and lab ranges, however will be based on their derived age.
- Age group (<65, \geq 65 years old)
- Age group (<65, \geq 65 to <75, \geq 75 to <85, \geq 85 years old)
- Body Mass Index (BMI) (kg/m^2) = $\text{Weight}(\text{kg})/((\text{Height}(\text{cm})/100)^2)$
- BMI category (<25 kg/m^2 , \geq 25 to <30 kg/m^2 , \geq 30 kg/m^2)
- The duration of AD from diagnosis (years) = [(Date of informed consent – Date of AD diagnosis)+1]/ 365.25.
 - If year of onset is missing, duration of AD will be set as missing. Otherwise, unknown month will be taken as January, and unknown day will be taken as 01. The duration of AD will be rounded to 1 decimal place.
- Duration of AD (years) category (0 to <2 years, 2 to < 5 years, 5 to <10 years, 10 to <20 years, \geq 20 years)
- Diagnosis age (years), derived using diagnosis date as the reference start date and July 1st of birth year and truncated to a whole-integer age.
- Diagnosis age group (<18, \geq 18 to <50, \geq 50 years old)
- Change from baseline = postbaseline measurement at Visit x – baseline measurement.
 - If a baseline value is missing, it will not be imputed and the change from baseline will not be calculated.
- Percent change from baseline at Visit x:
 $((\text{Post-baseline measurement at Visit x} - \text{Baseline measurement})/\text{Baseline measurement}) * 100$.
 - If a baseline value is missing, it will not be imputed and percent change from baseline will not be calculated.
- Weight (kg) = weight (lbs) * 0.454.
- Weight category (<60 kg, \geq 60 to <100 kg, \geq 100 kg)
- Height (cm) = height (in) * 2.54.
- Cyclosporine inadequate efficacy (yes, no)
 - Set yes if the reason for discontinuation is inadequate response.

- Cyclosporine intolerance (yes, no)
 - Set **yes** if the reasons for discontinuation are: intolerance to medication or contraindication (Physician indicated cyclosporine was used and a contraindication was noted).
- Cyclosporine contraindication [ineligible] (yes, no)
 - Set to **yes** if cyclosporine never used because of a contraindication
- Cyclosporine inadvisable (yes, no)

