Work Productivity and Activity Impairment: Atopic Dermatitis (WPAI-AD)	The Work Productivity and Activity Impairment Questionnaire-Atopic Dermatitis (WPAI-AD) records impairment due to AD during the past 7 days. The WPAI-AD consists of 6 items grouped into 4 domains: absenteeism (work time missed), presenteeism (impairment at work/reduced on-the-job effectiveness), work productivity loss (overall work impairment/absenteeism plus presenteeism), and activity impairment. Scores are calculated as impairment percentages (Reilly et al. 1993), with higher scores indicating greater impairment and less productivity.	Employment status	Question (Q)1	Single item, missing if missing.
		Change in employment status	Employed at baseline and remained employed: Q1 = 1 at post-baseline visit and at baseline visit. Not employed at baseline and remain unemployed: Q1 = 0 at post-baseline visit and at baseline visit.	Missing if baseline or observed value is missing.
		Percentage of absenteeism	Percent work time missed due to problem: $(Q2/(Q2 + Q4)) * 100$	If Q2 or Q4 is missing, then missing.
		Change from baseline in absenteeism	Change from baseline: observed absenteeism – baseline absenteeism	Missing if baseline or observed value is missing.
		Percentage of presenteeism	Percent impairment (reduced productivity while at work) while working due to problem: $(Q5/10) * 100$	If Q5 is missing, then missing.
		Change from baseline in presenteeism	Change from baseline: observed presenteeism – baseline absenteeism	Missing if baseline or observed value is missing.
		Overall work impairment	Percent overall work impairment (combines absenteeism and presenteeism) due to problem: $(Q2/(Q2+Q4) + [(1 - Q2/(Q2+Q4)) * (Q5/10)]) * 100$	If Q2, Q4, or Q5 is missing, then missing.
		Change from baseline in work impairment	Change from baseline: observed work impairment – baseline work impairment	Missing if baseline or observed value is missing.

Measure	Description	Variable	Derivation / Comment	Imputation Approach if Missing Components
		Percentage of impairment in activities	Percent activity impairment (performed outside of work) due to problem: $(Q6/10)*100$	If Q6 is missing, then missing.
		Change from baseline in impairment in activities	Change from baseline: observed impairment in activities – baseline impairment in activities	Missing if baseline or observed value is missing.

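### The SAP computes WPAI presenteeism change by subtracting baseline absenteeism, so that change score is wrong as written

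*SAP*

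**What the plan says.** SAP Section 4.2.2 lists "Mean change in the WPAI scores at 16 weeks" among the other secondary endpoints, and protocol Section 4 does the same. Table JAHL.6.7 analyses observed values and change from baseline for four WPAI-AD scores (absenteeism, presenteeism, overall work impairment, activity impairment). The method is MMRM in the ITT population at Week 16, each dose against placebo, with ANCOVA on mLOCF data as sensitivity analysis.

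Table JAHL.6.6 gives the derivations. Presenteeism is item 5 divided by 10, times 100. Absenteeism is item 2 divided by the sum of items 2 and 4, times 100. The four change rows read:

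- Absenteeism: "Change from baseline: observed absenteeism – baseline absenteeism"
- Presenteeism: "Change from baseline: observed presenteeism – baseline absenteeism"
- Overall work impairment: "Change from baseline: observed work impairment – baseline work impairment"
- Activity impairment: "Change from baseline: observed impairment in activities – baseline impairment in activities"

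The general rule in SAP Section 6.2.4 is "Change from baseline = postbaseline measurement at Visit x – baseline measurement".

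**The concern.** The presenteeism row takes its follow-up value from one domain and its baseline from another, so the result is not a change from baseline in anything. It conflicts with the three neighbouring rows and with Section 6.2.4, and it looks like a copy from the absenteeism row.

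Section 6.12 names Table JAHL.6.6 as the place where these measures are derived, so a programmer could reasonably follow the specific row rather than the general rule. Both domains are percentages from 0 to 100, so a wrong value would look plausible and could pass unnoticed. At stake are the within-arm mean changes in presenteeism, the precision of the comparison with placebo, and possibly the set of patients analysed. Protocol Section 9.9 names WPAI-AD as one of two instruments for the health-economic evaluation, so these numbers have a use beyond the study report.

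**Working it through.** The plan gives no figure to reproduce. The documents also give no WPAI means, SDs or correlations, so every numerical input below is an assumption. The formulas are the SAP's.

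**Size of the error per patient.** Write P0 and P1 for presenteeism at baseline and follow-up, and A0 for baseline absenteeism.

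- Change with own baseline: P1 − P0
- Change as written: P1 − A0 = (P1 − P0) + (P0 − A0)

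The error is P0 − A0. Higher scores mean more impairment, so a positive change is a worsening.

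**Illustrative patients (assumed item values).**

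| Items 2 and 4 at baseline | Item 5, baseline to follow-up | A0 | P0 to P1 | Own baseline | As written |
|---|---|---|---|---|---|
| 4, 36 | 6 to 6 | 10 | 60 to 60 | 0 | +50 |
| 4, 36 | 6 to 3 | 10 | 60 to 30 | −30 | +20 |
| 20, 20 | 3 to 3 | 50 | 30 to 30 | 0 | −20 |

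The second patient halves the impairment and is recorded as worse. The third does not change and is recorded as better.

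**Within-arm means.** Assume mean P0 = 45, mean A0 between 5 and 20, and a true mean change of −5.

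- A0 = 5: −5 + (45 − 5) = +35
- A0 = 20: −5 + (45 − 20) = +20

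**Difference between arms.** P0 and A0 are both measured before treatment, so randomization gives the error P0 − A0 the same expectation in every arm. The expected treatment difference is unchanged; what changes is the residual variance. Suppose the model adjusts for baseline presenteeism, and A0 is related to P1 only through P0. Let r be the correlation of P0 with P1, and ρ the correlation of P0 with A0. Then

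SE ratio (written / own baseline) = √[1 + SD(A0)²(1 − ρ²) / {SD(P1)²(1 − r²)}].

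With SD(P1) = 25, SD(A0) = 20 and r = 0.5, the denominator is 625 × 0.75 = 468.75.

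- ρ = 0.2: √(1 + 400 × 0.96 / 468.75) = √1.819 = 1.35
- ρ = 0.6: √(1 + 400 × 0.64 / 468.75) = √1.546 = 1.24

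A simulation with these SDs and the same range of ρ (240 versus 120 patients, ANCOVA on baseline presenteeism) gave ratios of 1.21 to 1.36.

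A second simulation used a smaller absenteeism SD: baseline means 50 and 10, SDs 25 and 15, residual SD of P1 equal to 20, true difference −10, 240 versus 120 patients.

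| ρ | Difference, own baseline | Difference, as written | SE, own baseline | SE, as written | SE ratio |
|---|---|---|---|---|---|
| 0.2 | −10.00 | −9.93 | 2.23 | 2.77 | 1.24 |
| 0.5 | −10.03 | −10.02 | 2.24 | 2.67 | 1.19 |
| 0.8 | −10.03 | −10.08 | 2.24 | 2.45 | 1.09 |

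The placebo mean change was about +35 as written, against −5 with own baseline.

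**Missing data.** The row makes the change missing if the baseline or the observed value is missing. If baseline means absenteeism, that value is missing when item 2 or item 4 is missing, and undefined when both are zero. Presenteeism needs only item 5. The documents give no basis for the number of patients affected.

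**The case against.** The intended rule can be recovered from the SAP itself. The variable is named as change in presenteeism, Section 6.2.4 gives the right definition, and the adjacent rows follow it. Nothing shows that the row was programmed literally. This stands, and it limits the finding to the plan as written.

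Only one of four WPAI change scores is affected. Overall work impairment and observed presenteeism are derived correctly, WPAI is not adjusted for multiplicity, and no primary, key secondary or safety analysis is touched. This also stands.

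The treatment comparison is partly protected. Table JAHL.6.7 also fits the MMRM to observed presenteeism. If the baseline covariate there is baseline presenteeism, with its interaction with visit, that model gives the same arm difference as the correct change-score model. So a valid estimate is already planned alongside the faulty one. It does not repair the reported change scores or their within-arm means.

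The loss of precision depends heavily on assumptions. In the formula above, with SDs of 25 and 20 and ρ from 0.2 to 0.6, moving r over 0.3 to 0.7 gives an increase of 20% to 48%. If literal coding also made absenteeism the baseline covariate, the range would be 3% to 39%. The checks used ANCOVA and all randomized patients, whereas the planned main analysis is MMRM and presenteeism applies to people who are working. The direction is firm; the percentage is not.

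**Conclusion.** The concern holds. The derivation of presenteeism change contradicts both Section 6.2.4 and the other WPAI rows, and it feeds a pre-specified Week 16 secondary analysis.

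That each patient's change is off by baseline presenteeism minus baseline absenteeism is exact and needs no assumption. A reported worsening of 20 to 35 points in place of a 5-point improvement rests on assumed baseline means. The rise in standard error (about 21% to 36% with SDs of 25 and 20, about 9% to 24% with the smaller absenteeism SD) rests on assumed SDs and correlations. The treatment difference is not expected to be biased.

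The row should be corrected, but the trial's main conclusions do not depend on it. The documents do not establish that any reported result is wrong.

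**What to change.** In Table JAHL.6.6, define change from baseline in presenteeism as observed presenteeism minus baseline presenteeism, missing only if one of those two values is missing. Then check that the analysis dataset specification and the program use baseline presenteeism, both in the change score and as the baseline covariate in the MMRM and ANCOVA. The cost is one word in the SAP and a short programming check; no data collection or design feature changes. If results have already been produced, confirm which derivation was used and rerun the presenteeism change outputs if it was the written one.

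### WPAI overall work impairment is set to missing when Q5 is blank, even where Q4 = 0 and Q2 > 0 and the SAP's own formula already fixes the score at 100%

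*SAP*

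**What the plan says.** SAP section 4.2.2 lists "Mean change in the WPAI scores at 16 weeks" among the other secondary endpoints, which are not adjusted for multiplicity. Table JAHL.6.7 analyses four WPAI-AD measures: absenteeism, presenteeism, overall work impairment and activity impairment.

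Table JAHL.6.6 gives the derivations and missing-item rules:

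- Absenteeism is Q2 as a percentage of Q2 + Q4. Its rule is "If Q2 or Q4 is missing, then missing".
- Presenteeism comes from Q5 alone, described as "Percent impairment (reduced productivity while at work) while working due to problem".
- Overall work impairment combines the two. Its rule is "If Q2, Q4, or Q5 is missing, then missing", with no exception for Q4 = 0.
- Activity impairment comes from Q6 alone.

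WPAI scores run from good to bad, "with higher scores indicating greater impairment and less productivity", so 100% is the worst value. On baseline, section 6.2.4 says: "If a baseline value is missing, it will not be imputed and the change from baseline will not be calculated".

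**The concern.** From the absenteeism formula, Q2 is working time lost to AD and Q4 is time worked. A patient with Q2 > 0 and Q4 = 0 has lost all working time to AD. That patient has no time at work on which to rate productivity, so a blank Q5 would be natural. The missing-item rule would then remove a score that needs no Q5, and that score is the highest possible.

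If this happens at baseline, the patient has no change score in this variable at any visit. If it happens later, that visit is missing because the score is at its maximum, which strains the missing-at-random assumption of the MMRM (SAP 6.4.2). The sensitivity analysis planned for WPAI, ANCOVA with mLOCF, does not repair this: it carries forward an earlier post-baseline value, which cannot be worse than 100%. Tables JAHL.6.1 and JAHL.6.7 plan neither placebo multiple imputation nor a tipping-point analysis for WPAI. Protocol section 9.9 also names WPAI-AD as one of two instruments for health economics, where complete loss of work matters.

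**Working it through.** The documents give no numerical result for this rule, so there is no stated figure to reproduce.

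**Step 1: the formula.** Let A = Q2/(Q2 + Q4). Table JAHL.6.6 then gives overall work impairment = 100 × [A + (1 − A) × Q5/10]. Over Q5 = 0 to 10:

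| Q2 | Q4 | A | Score, lowest to highest |
|---|---|---|---|
| 40 | 0 | 1 | 100 to 100 |
| 8 | 0 | 1 | 100 to 100 |
| 1 | 0 | 1 | 100 to 100 |
| 39 | 1 | 0.975 | 97.5 to 100 |
| 20 | 20 | 0.5 | 50 to 100 |
| 0 | 40 | 0 | 0 to 100 |
| 0 | 0 | 0/0 | undefined |

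Q5 is irrelevant only when Q4 = 0 and Q2 > 0. In every other defined case it is needed. With Q2 = Q4 = 0 the score does not exist even if all items are answered.

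**Step 2: one record, two rows.** Take Q2 = 40, Q4 = 0, Q5 blank. Absenteeism = 100 × 40/(40 + 0) = 100%. Overall work impairment is missing, although it combines absenteeism with presenteeism and equals 100% for any Q5.

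**Step 3: effect on a visit mean (illustration).** Suppose a share s of workers is in this state with Q5 blank and the rest average m. The mean with them kept is (1 − s) × m + s × 100. Dropping them gives m, which is too low by s × (100 − m). Both s and m are assumed.

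| s | m = 30: kept (shortfall) | m = 50: kept (shortfall) |
|---|---|---|
| 1% | 30.7 (0.7) | 50.5 (0.5) |
| 2% | 31.4 (1.4) | 51.0 (1.0) |
| 5% | 33.5 (3.5) | 52.5 (2.5) |
| 10% | 37.0 (7.0) | 55.0 (5.0) |

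**Step 4: effect on the treatment difference (illustration).** Assume Week 16 means among the other workers of 38 on placebo and 28 on active, with affected shares p and q. The difference with everyone kept is (28 + 72q) − (38 + 62p) = −10 + 72q − 62p. With them dropped it is −10.0.

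| p (placebo) | q (active) | Kept |
|---|---|---|
| 1% | 0.5% | −10.3 |
| 2% | 1% | −10.5 |
| 4% | 2% | −11.0 |
| 2% | 2% | −9.8 |
| 4% | 4% | −9.6 |

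The two agree when 72q = 62p, that is q = 0.86p. Below that ratio, dropping these patients understates the benefit; above it, dropping them overstates it. These are raw Week 16 means, not the planned baseline-adjusted MMRM, so they show direction only.

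**The case against.** The strongest reply is that the problem exists only if Q5 is blank when no hours were worked, and neither document reproduces the questionnaire or its skip pattern. If Q5 is answered, the formula returns 100% and nobody is lost. The item-level missing rules do not prove a skip either, since patients without employment also need one. This stands. The evidence for a blank Q5 is indirect: Q5 is described as a rating of time at work, and WPAI has item-level rules where the HADS and DLQI rows say partial assessments cannot be saved.

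Three further replies stand in part:

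- The loss is narrow. The patient keeps absenteeism at 100% and the activity score. A post-baseline blank loses one variable at one visit, and WPAI-AD is collected at Weeks 0, 1, 2, 4, 8, 12 and 16.
- The primary censoring rule (SAP 6.4) already removes values after rescue or permanent study drug discontinuation. Affected patients in that position would not be restored in the main analysis.
- Comparability with the instrument's published scoring cannot be judged without that source. However, the SAP formula already gives 100% to the same record whenever Q5 is filled in.

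A reader might infer that the most impaired workers leave the WPAI endpoint altogether, or that the rule biases the treatment effect in one direction. The documents support neither: the other measures remain, and the sign depends on the unknown split between arms.

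**Conclusion.** The point holds as a minor, conditional one. What is certain is that the rule can discard a score that the SAP's own formula fully determines, and that this score is the maximum. The same record is scored 100% in the absenteeism row.

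What follows in practice rests on Q5 being left blank when Q4 = 0 and Q2 > 0. Under that assumption, visit means of overall work impairment are understated and missingness depends on the score itself. The size is s × (100 − m), or 0.5 to 7.0 points over the assumed ranges. The documents give no figure for s, and it is probably small. No direction can be claimed for the treatment difference. The variable is one of four WPAI measures within an objective that has no multiplicity control, so no primary or key secondary conclusion is affected.

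**What to change.** Replace the missing-item rule for overall work impairment in Table JAHL.6.6 with:

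1. If Q4 = 0 and Q2 > 0, the score is 100% regardless of Q5.
2. If Q2 = Q4 = 0, the score is missing, because the formula is 0/0.
3. In all other cases, keep the present rule.

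Leave presenteeism missing when Q5 is missing.

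The cost is one line in the derivation table and the matching line of code, best settled before unblinding. It is a derivation from collected items rather than an imputation, applies alike in all arms, and changes nothing if Q5 is never blank in this state. A count by arm and visit of records meeting condition 1 with Q5 blank would show how much it matters.

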6.13. Bioanalytical and Pharmacokinetic/Pharmacodynamic Methods

Pharmacokinetic (PK), Pharmacodynamic (PD) and Biomarker analyses to address secondary and exploratory objectives of this study will be described by Lilly in separate PK/PD and Biomarker analysis plans.

6.14. Safety Analyses

The general methods used to summarize safety data, including the definition of baseline value are described in Section 6.2.

Safety analyses will include data before and after rescue, unless otherwise stated, and patients will be analyzed according to the investigational product to which they were randomized at Visit 2. A sensitivity approach to the safety analyses will use data censored at last dose of the study drug for patients rescued to systemic therapy. These analyses will be conducted for treatment-emergent adverse events (TEAEs), serious adverse events (SAEs), AEs leading to permanent study drug discontinuation and special topics excluding deaths and malignancies. Additional analyses may be conducted using data after rescue to systemic therapy for some safety topics such as systemic TEAEs, and SAEs. Safety analyses will take place using the safety population defined in Section 6.2.1.

Safety topics that will be addressed include the following: AEs, clinical laboratory evaluations, vital signs and physical characteristics, Columbia Suicide Severity Rating Scale (C-SSRS), the Self-Harm Supplement Form, safety in special groups and circumstances, including adverse events of special interest (AESI) (see Section 6.14.5), and investigational product interruptions.

Unless otherwise specified, by-visit summaries will include planned on-treatment visits. For tables that summarize events (such as AEs, categorical lab abnormalities, shift to maximum value), post-last dose follow-up data will be included. Follow-up data is defined as all data occurring up to 30 days (planned maximum follow-up time) after last dose of treatment including rescue, regardless of study period. Listings will include all safety data.

For selected safety assessments other than events, descriptive statistics may be presented for the last measure observed during post-treatment follow-up (up to 30 days after the last dose of treatment including rescue, regardless of study period).

